6. BASELINE, EXPOSURE, AND DISPOSITION

[Appendix A](#) provides a list of data displays. Sample data displays are included in a separate document.

6.1. Baseline and Demographics, Physical Characteristics, and Disease History

6.1.1. Demographics and Baseline Characteristics

The following demographics characteristics will be summarized for the safety population: age, sex, race, ethnicity, weight, and height.

6.1.2. Baseline Disease Characteristics

The following baseline disease characteristics will be summarized for the safety population: ECOG performance status, baseline parathyroid hormone, and baseline phosphate.

6.1.3. Disease History

For those who have solid tumor cancer history in the safety population, time since diagnosis, solid tumor cancer type, TNM classification at diagnosis and baseline, current stage, current sites of disease, and tumor marker test result will be summarized.

For those who have glioblastoma cancer history in the safety population, time since diagnosis, basis of initial diagnosis, time since reoccurrence, initial and current tumor WHO grade, infratentorial, supratentorial and CSF involvement at diagnosis and baseline, cerebral hemisphere involvement at diagnosis and baseline, multifocal disease at baseline and current sites of disease, and MGMT status will be summarized.

Time since diagnosis will be calculated as follows:

$$\text{Time since diagnosis (years)} = (\text{Day 1 date} - \text{date of diagnosis} + 1) / 365.25.$$

Time since reoccurrence will be calculated as follows:

$$\text{Time since reoccurrence (months)} = (\text{Day 1 date} - \text{date of reoccurrence} + 1) / 30.44.$$

6.1.4. Prior Therapy

The number of prior systemic cancer therapy regimens will be summarized for all participants in the safety population. The component drugs of prior systemic therapy regimens will be coded using the WHO Drug Dictionary. Number and percentage of participants with each drug will be summarized by WHO drug class and WHO drug PT. Regimen name, component drugs, start and stop date, purpose of the regimen, best response, reason for discontinuation, and date of relapse/progression will be listed.

The number of participants who received prior radiation will be summarized for the safety population. Radiotherapy type, body site, reason for regimen, start and stop date, total dose, and best response will be listed.

The number of participants who received prior radiotherapy for glioblastoma will be summarized for the safety population. Body type, start and stop date, total dose, radiation therapy technique, radiation method, and best response will be listed.

The number of participants who had prior surgery or surgical procedure for disease under study and for glioblastoma will be summarized for the safety population. Date and description of the surgery/procedure will be listed for disease under study and glioblastoma, extent of resection for glioblastoma will also be listed.

The number of participants who had prior loco-regional therapy will be summarized for the safety population. Therapy/treatment name, start and stop date, best response, reason for discontinuation and date of relapse/progression will be listed.

6.1.5. Medical History

For participants in the safety population, medical history will be summarized by assigned cohort. This summation will include the number and percentage of participants with significant medical history for each body system/organ class as documented on the eCRF.

6.2. Disposition of Participant

The number and percentage of participants who were treated, who were ongoing with study treatment, who discontinued study treatment with a primary reason for discontinuation, who were still in study, and who withdrew from the study with a primary reason for withdrawal will be summarized for the safety population.

The number and percentage of participants who were screened and enrolled will be summarized.

6.3. Protocol Deviations

Protocol deviations recorded on the eCRF will be summarized and listed.

6.4. Exposure

For participants in the safety population, exposure to pemigatinib will be summarized descriptively as the following:

- **Number of treatment cycles:** Number of cycles with a nonzero dose of pemigatinib.
- **Duration of treatment with pemigatinib (days):**
Date of last dose of pemigatinib – date of first dose of pemigatinib + 1.
- **Average daily dose of pemigatinib (mg/day):**
Total actual pemigatinib dose taken (mg) / duration of treatment with pemigatinib (days).
- **Pemigatinib dose modifications:** Number of participants who had pemigatinib dose reduction, and interruption will be summarized.

6.5. Study Drug Compliance

For participants in the safety population, overall compliance (%) for pemigatinib will be calculated for all participants as

$$\text{Compliance (\%)} = 100 \times [\text{total dose actually taken}] / [\text{total prescribed dose}].$$

The total prescribed dose is defined as the sum of the doses prescribed by the investigator accounting for dose modifications.

The total actual dose taken will be calculated based on information entered on the Drug Accountability eCRF. If there are dispensed drugs that have not been returned yet, the actual dose taken starting from the dispense date of the unreturned drugs will be imputed by the dose taken as reported on the Dosing eCRF.

6.6. Prior and Concomitant Medication

Prior medications and concomitant medications will be coded using the WHO Drug Dictionary. Number and percentage of participants in the safety population for each prior and concomitant medications will be summarized by WHO drug class and WHO drug PT.

7. EFFICACY

[Appendix A](#) provides a list of data displays. Sample data displays are included in a separate document.

7.1. Efficacy Hypotheses

Objective Response Rate (Primary Endpoint): Administration of pemigatinib to participants in Cohort A and B improves ORR from 15%. Assume ORR_A and ORR_B are the ORRs for cohort A and B respectively.

The hypotheses for Cohort A are as follows:

- H_0 (null hypothesis): $ORR_A \leq 15\%$
- H_A (alternative hypothesis): $ORR_A > 15\%$

The hypotheses for cohort B are as follows:

- H_0 (null hypothesis): $ORR_B \leq 15\%$
- H_A (alternative hypothesis): $ORR_B > 15\%$

7.2. Analysis of the Primary Efficacy Parameter

7.2.1. Primary Efficacy Analysis

The primary endpoints of the study are ORR in Cohort A and Cohort B, respectively. Objective response rate is defined as the proportion of participants who achieved a CR or a PR based on RECIST v1.1 or RANO, as assessed by an independent centralized radiological review committee. Confirmation of CR and PR is required and documented in the Independent Central Review Charter. This analysis will be based on the efficacy evaluable population. Participants

who do not have sufficient baseline or on-study response assessment information to be adequately assessed for response status will be included in the denominators in the calculation of ORR. The 95% CI for the ORR will be estimated using the Clopper-Pearson method. The p-value from the exact binomial test will be provided.

The ORR will also be analyzed based on the PP population as a sensitivity analysis.

7.2.1.1. Response Criteria

Overall disease status will be categorized using RECIST v1.1 ([Eisenhauer et al 2009](#)) and RANO. Participants will have their overall response evaluated as CR, PR, SD, PD, or NE at each postbaseline radiological assessment. Assessments using RECIST v1.1 are based on changes in target lesions, nontarget lesions, and appearance of new lesions. Assessments using RANO are based on enhancing measurable lesions, enhancing nonmeasurable/nontarget lesions, nonenhancing T2/FLAIR/nontarget lesions, new lesions, steroid use, and clinical status.

7.2.1.2. Objective Response Rates and Best Overall Response

A participant is considered an objective responder if they have a best overall response of CR or PR at any postbaseline visit before first PD.

In general, under RECIST v1.1 and RANO, best overall response is the best response recorded postbaseline before and including the first PD, in the order of CR, PR, SD, PD, and NE. The best overall response will be determined from response assessments before or on the same day as new anticancer therapy. If any alternative cancer therapy is taken while on study, any subsequent assessments will be excluded from the best overall response determination.

In the case of SD, measurements must meet the SD criteria at least once after the date of first dose at a minimum interval of 42 days. Participants who fail to meet this criterion will have best overall response of PD if the next available assessment indicates PD or NE if there is no additional assessment available.

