## **8.2. Efficacy Assessments**

### **8.2.1. Tumor Imaging**

Objective assessment of tumor status is required using appropriate disease-specific techniques, and a central radiologic facility will be used to determine responses and will be logged in to the eCRF. RECIST v1.1 ([Eisenhauer et al 2009](#)), and RANO for participants with primary brain tumors, will be used, and the recommended method for measuring and following tumor burden will be CT scan to include the thorax, abdomen, and pelvis; the neck can be included if needed. Alternative modalities (eg, MRI) may be substituted for a CT scan at the discretion of the investigator, provided that the same modality is used throughout the study and that the methodology is consistent with RECIST v1.1 or RANO.

The schedule for efficacy assessments will be at screening (this will be considered the baseline scan), every 9 weeks (every 3 cycles), and then at EOT (if applicable). Imaging should continue in 9-week intervals regardless of delays in cycle starts. For participants showing a response, a confirmatory scan may be performed a minimum of 4 weeks (per RECIST v1.1 and RANO) from the previous scan. For participants showing a progression based on local radiologic review, treatment should not be discontinued until progression of disease has been determined by the ICR, unless the principal investigator believes it is in the best interest of the participant to discontinue treatment before receiving confirmation.

For participants who discontinue treatment for reasons other than disease progression, every effort should be made to continue monitoring their disease status by radiographic imaging until 1) start of new anticancer therapy, 2) documented disease progression, 3) death, or 4) end of study, whichever occurs first.

[figure not shown]

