3.2. Control of Type I Error

For the primary endpoint, the overall 1-sided Type I error is 0.025. The primary endpoint in Cohort A and Cohort B will be tested sequentially at 1-sided 0.025. If ORR in Cohort A is significant, then ORR in Cohort B will be tested.

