7.3.2. Duration of Response

For objective responders, the duration of response is defined as the time from the date that a participant first achieves CR or PR based on RECIST v1.1 or RANO as assessed by ICR, until the date of first documented disease progression based on RECIST v1.1 or RANO as assessed by ICR, or death. Partial death dates will be handled using the rules described in Section [4.1.4](#).

Participants who are alive without progression before analysis cutoff date will be censored.

Censoring of DOR will follow the same algorithm as the censoring of PFS (see Section [7.3.1](#)).

Duration of response data will be analyzed by the Kaplan-Meier method in Cohorts A and B, respectively. The total number of responders, the number of participants who progressed or died, and the number of participants censored will be summarized. The KM estimate of median DOR will be presented with its 95% CI. The 95% CI will be calculated using the generalization of Brookmeyer and Crowley's method (1982) with log-log transformation (Klein and Moeschberger 1997).

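### Does SAP 7.2.1.2 let unconfirmed responses count in the primary ORR, when SAP 7.2.1 requires confirmation?

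*SAP*

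**What the plan says.** SAP 7.2.1 (Primary Efficacy Analysis) defines ORR as the proportion with CR or PR by independent central review, then adds: "Confirmation of CR and PR is required and documented in the Independent Central Review Charter". Participants who cannot be assessed for response stay in the denominator.

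SAP 7.2.1.2, a subsection of 7.2.1, gives the derivation. Its rule for responders reads: "considered an objective responder if they have a best overall response of CR or PR at any postbaseline visit before first PD". The ranking comes next, framed as a general statement about the two sets of response criteria: "best overall response is the best response recorded postbaseline before and including the first PD", with CR highest, followed by PR, SD, PD and NE. Later treatment is handled: "The best overall response will be determined from response assessments before or on the same day as new anticancer therapy". The only reclassing rule concerns SD that misses a 42-day minimum: "Participants who fail to meet this criterion will have best overall response of PD if the next available assessment indicates PD or NE", the last when no further assessment exists. Confirmation is not repeated here.

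SAP 7.3.2 takes its population from the same set: "For objective responders, the duration of response is defined as the time from the date that a participant first achieves CR or PR". SAP 3.2 orders the tests: "If ORR in Cohort A is significant, then ORR in Cohort B will be tested".

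Protocol 10.4.1 defines ORR without mentioning confirmation. Protocol 8.2.1 says that for responders "a confirmatory scan may be performed a minimum of 4 weeks (per RECIST v1.1 and RANO) from the previous scan".

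**The concern.** A programmer usually works from the derivation section. Section 7.2.1.2 reads like a complete algorithm: a ranking, a cut at first progression, a cut at new therapy and a minimum duration for SD. It sets no condition of persistence for CR or PR, the two categories that decide the primary test. Taken alone, PR at one scan and PD at the next yields a responder, whereas 7.2.1 says that response does not count. The protocol does not settle the matter, since its ORR definition is silent and its confirmatory scan is optional.

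The tested count could then exceed the confirmed count, and one responder is enough to move either cohort across its boundary. Duration of response would also take in short, unconfirmed responses, because it is restricted to the same objective responders.

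**Working it through.** **Inputs from the documents.** Null ORR 15% (SAP 7.1); one-sided 0.025, Cohort A before Cohort B (SAP 3.2); N = 60 with true ORR 35%, N = 90 with true ORR 30%, each with at least 90% power (SAP 3.3); exact binomial test (SAP 7.2.1). **Assumed:** the share u of responses that are never confirmed. The documents do not give it; u = 5% to 10% is used.

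**1. Reproduce the plan.** The boundary is the smallest r with P(X ≥ r | N, 0.15) ≤ 0.025.

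| Cohort | Boundary | p at boundary | p one responder lower | Power at planning rate |
|---|---|---|---|---|
| A | 16/60 | 0.0136 | 0.0291 (15/60) | 93.4% |
| B | 21/90 | 0.0240 | 0.0434 (20/90) | 93.5% |

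The stated power of at least 90% holds in both. These values depend only on N, the null, the level and the planning rates. With 35% and 30% taken as confirmed rates, none of them changes.

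**2. What the literal reading of 7.2.1.2 would do.** If unconfirmed responses were counted, a confirmed rate p would be tested as p/(1−u). At p = 0.15 this is 0.1579 (u = 5%) or 0.1667 (u = 10%).

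| Quantity | Confirmed rule | u = 5% | u = 10% |
|---|---|---|---|
| A rejects, confirmed ORR 15% | 1.4% | 2.1% | 3.4% |
| B rejects if tested, confirmed ORR 15% | 2.4% | 3.9% | 6.4% |
| A at 35%, B at 15%: false claim in B | 0.9344 × 0.0240 = 2.2% | 0.9641 × 0.0395 = 3.8% | 0.9830 × 0.0643 = 6.3% |
| Extra responders in A at 35%: 60 × 0.35 × u/(1−u) | 0 | 1.1 | 2.3 |
| Extra responders in B at 30%: 90 × 0.30 × u/(1−u) | 0 | 1.4 | 3.0 |
| Verdicts that differ, A at 35% | 0 | 3.0% | 4.9% |
| Verdicts that differ, B at 30%, if tested | 0 | 3.1% | 5.0% |

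Between null and planning rates the difference is larger: 9.3-19.3% in A at 25%, and 8.6-19.0% in B at 20%. A's error passes 2.5% once u exceeds 6.7%; B's, with A at 35%, at about 1.0%.

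**3. Does the plan lead there?** Set the two sections side by side:
- 7.2.1 states which CR and PR qualify, without exception, and names the document holding the detail.
- 7.2.1.2 ranks the recorded responses, in a sentence introduced as a general statement under RECIST v1.1 and RANO. Nowhere does it say that an unconfirmed response counts.

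Read together they do not conflict: the parent section sets the condition and the subsection orders what meets it. Every inflated figure in step 2 requires the analyst to set aside an explicit sentence in the parent section.

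**4. Can confirmation be obtained?** Protocol 8.2.1 schedules imaging every 9 weeks, with a 7-day window in Protocol Table 3. Consecutive scheduled scans are therefore at least 63 − 14 = 49 days apart, beyond the 28-day minimum for a confirmatory scan. A routine scan can confirm, so the optional extra scan does not undermine the requirement.

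**5. Does the missing class matter to the test?** An unconfirmed CR or PR becomes SD, PD or NE. Each is a non-response, and 7.2.1 keeps the participant in the denominator. The choice moves people between rows of the best-response table and leaves the ORR, its interval and its p-value unchanged.

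**The case for a change.** The strongest case for a change is that an SAP exists to supply derivations, and the primary endpoint should be derivable from it without consulting a second document. Section 7.2.1.2 sets a minimum duration for SD but not for CR or PR, and does not point back to the Charter. The margin is one responder, and B's false-claim rate is sensitive to even a small unconfirmed share. Two or three sentences would remove any doubt.

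Part of this stands. The subsection does not repeat the requirement, and the SAP itself leaves the class of an unconfirmed response unstated. A cross-reference would be tidier. But it would leave the tested quantity, the boundaries and the power as they are, since 7.2.1 already fixes the endpoint. Writing a particular interval and fallback class into the SAP has its own risk. The Charter was not available here; if it differs, the added text would create the contradiction it was meant to remove. Duration of response needs nothing further: its start is already the first CR or PR, and its population follows from the responder definition.

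**Conclusion.** No change to the plan follows. The primary endpoint is confirmed ORR under SAP 7.2.1, and 7.2.1.2 is a subsection that leaves a condition of its parent unrepeated. This is a drafting gap that an analyst reading the whole of 7.2.1 fills correctly. Boundaries (16/60 and 21/90), exact levels (0.0136 and 0.0240) and power (93.4% and 93.5%, taking the planning rates as confirmed rates) stand.

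The error inflation and the 3-5% of differing verdicts at the planning rates rest on two conditions together: that 7.2.1 is disregarded in programming, and that 5-10% of responses are unconfirmed, a share the documents do not give. The conclusion also relies on the Charter specifying how confirmation is applied, as 7.2.1 says it does. Whether it assigns a class to unconfirmed responses could not be checked, but that class affects only the best-response breakdown.

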7.2.2. Subgroup Analyses for Primary Endpoint

Subgroup analysis of the primary endpoint will be performed based on appropriate intrinsic and extrinsic factors if needed.

7.2.3. Sensitivity and Supportive Analyses for Primary Endpoint

The ORR will be analyzed based on the PP population as a sensitivity analysis.

7.3. Analysis of the Secondary Efficacy Parameters

7.3.1. Progression-Free Survival

Progression-free survival is defined as the time from date of first dose of study drug to the earliest date of PD or death, whichever is first. Progressive disease is evaluated based on RECIST v1.1 or RANO, by the ICR. Partial death dates will be handled using the rules described in Section [4.1.4](#). Participants who are alive without progression before analysis cutoff date will be censored. Censoring for PFS will follow the algorithm outlined in [Table 2](#), which is

based on the FDA Guidance for Industry: Clinical Trial Endpoints for the Approval of Cancer Drugs and Biologics ([FDA 2015](#), [FDA 2018](#)).

Table 2: Evaluation and Censoring of Progression-Free Survival

Situation	Outcome	Date of Progression or Censoring
No baseline tumor assessments	Censored	Day 1
No valid postbaseline response assessments	Censored	Day 1
Progression documented between scheduled response assessments	Progressed	Date of first overall response of PD
No progression	Censored	Date of last valid radiologic assessment (not NE and not missing)
Study discontinuation for undocumented progression	Censored	Date of last valid radiologic assessment (not NE and not missing)
Study discontinuation for toxicity or other reason	Censored	Date of last valid radiologic assessment (not NE and not missing)

Table 2: Evaluation and Censoring of Progression-Free Survival (Continued)

Situation	Outcome	Date of Progression or Censoring
New anticancer treatment started	Censored	Date of last valid radiologic assessment (not NE and not missing) on/before starting a new anticancer treatment
Death before first progressive response assessment	Progressed	Date of death
Death between adequate response assessments	Progressed	Date of death
Death or progression after 2 or more missed assessments	Censored	Date of last valid radiologic assessment (not NE and not missing)

NE = not evaluable.

Progression-free survival data will be analyzed by the Kaplan-Meier method in Cohorts A and Cohort B, respectively. The number of participants who progressed or died and the number of participants censored will be summarized. The KM estimate of median PFS will be presented with its 95% CI. The 95% CI will be calculated using the generalization of Brookmeyer and Crowley's method ([1982](#)) with log-log transformation ([Klein and Moeschberger 1997](#)).

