**Table 16: Populations for Analysis**

Population	Description
Efficacy evaluable	
The efficacy evaluable population includes all enrolled participants in Cohorts A, B, and C who received at least 1 dose of study drug.
 
The efficacy evaluable population will be used for the summary of demographics, baseline characteristics, participant disposition, and analyses of all efficacy data.

Safety	The safety population includes all enrolled participants who received at least 1 dose of study drug. All safety analyses will be conducted using the safety population.
Per protocol	The per protocol population includes all efficacy evaluable population participants who are sufficiently compliant with the Protocol.
RECIST/RANO evaluable	
The RECIST/RANO evaluable population includes all efficacy evaluable population participants who have at least 2 objective tumor response assessments per independent centralized radiological review or who discontinued from the study or who discontinued from treatment without post-treatment tumor assessments.
 
RECIST/RANO evaluable population will be used for ORR analysis in the interim.

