2.2. Study Objectives and Endpoints

[Table 1](#) presents the objectives and endpoints.

Table 1: Objectives and Endpoints

Objectives	Endpoints
Primary	

• To evaluate the efficacy of pemigatinib in participants with locally advanced/metastatic or surgically unresectable solid tumor malignancy with an activating FGFR mutation or translocation.	
• ORR in Cohort A, defined as the proportion of participants in Cohort A who achieve a CR or PR based on RECIST v1.1 or RANO.• ORR in Cohort B, defined as the proportion of participants in Cohort B who achieve a CR or PR based on RECIST v1.1 or RANO.• An independent radiological review committee will determine response.

Table 1: Objectives and Endpoints (Continued)

Objectives	Endpoints
Secondary	

• To evaluate other clinical efficacy measurements of pemigatinib in participants with locally advanced/metastatic or surgically unresectable solid tumor malignancy with an activating FGFR mutation and/or translocation.• Safety and tolerability of pemigatinib.	
• PFS, defined as the time from first dose until PD (according to RECIST v1.1 or RANO and assessed by an ICR) or death (whichever is first) in Cohorts A and B, respectively.• DOR, defined as the time from the date of first assessment of CR or PR until the date of the first PD by an ICR per RECIST v1.1 or RANO, or death (whichever is first) in Cohorts A and B, respectively.• OS, defined as the time from first dose of study drug to death of any cause in Cohorts A and B, respectively.• Safety and tolerability, as assessed by the occurrence of TEAEs and treatment-related AEs according to NCI CTCAE v5.0, physical exam changes, vital sign changes, laboratory evaluations, and ECGs in each cohort.

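### For a death with no valid postbaseline scan, fewer than two missed scans and no new anticancer treatment, SAP Table 2 both censors PFS at Day 1 and counts an event

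*SAP*

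**What the plan says.** SAP section 7.3.1 makes Table 2 the censoring algorithm for PFS. Four of its rows matter here:

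- "No valid postbaseline response assessments": censored at Day 1, which SAP section 4.1.1 sets as the date of first dose.
- "Death before first progressive response assessment": an event on the date of death.
- "Death or progression after 2 or more missed assessments": censored at the last valid radiologic assessment.
- "New anticancer treatment started": censored at the last valid radiologic assessment on or before the new treatment.

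The table has no order of precedence and no footnote that chooses between rows.

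The surrounding text treats death as an event. SAP Table 1 has "PFS, defined as the time from first dose until PD" or death, whichever comes first, and section 7.3.1 repeats this. The sentence above Table 2 reads "Participants who are alive without progression before analysis cutoff date will be censored"; Protocol section 10.4.2 has the same sentence. All dosed participants enter the analysis (SAP section 5.3.1), so someone who dies before any scan is included.

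**The concern.** A participant who dies early, before any scan, fits two rows that give opposite outcomes. One row removes the participant from the risk set at Day 1; the other counts an event. Two programmers could both follow the SAP and report different event counts, censored counts and Kaplan-Meier curves from the same data, all of which section 7.3.1 asks for.

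The two readings do not err in the same direction. Applying the Day 1 row drops the earliest failures, so the later part of the curve is too high. In an open-label single-arm study, that choice should not wait until the data have been seen.

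The row for a missing baseline assessment also censors at Day 1 and has the same overlap. It should be nearly empty, because measurable disease is an entry criterion (Protocol section 5.1).

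**Working it through.** **Which rows apply.** The plan has no figure to reproduce, since PFS has no sample size or test. I applied the Table 2 rows as worded to participants who have a baseline scan, no valid postbaseline assessment and no documented PD. Scans are every 9 weeks (Protocol section 8.2.1), so a second missed scan falls at about week 18.

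| Case | Day 1 row | Death row | Another specific censoring row |
|---|---|---|---|
| Dies at week 6 | censored | event | none |
| Dies at week 12, one scan missed | censored | event | none |
| Dies at week 22, two scans missed | censored | event | missed-assessments row |
| New anticancer treatment, then dies | censored | event | new-treatment row |
| Alive | censored | does not apply | none |

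The contradiction to be corrected is in the first two cases. There the PFS definition counts the death, and the censoring sentence does not cover someone who has died, so the death row should govern. In the third and fourth cases Table 2 has a separate rule that censors, so a censored outcome is not shown to be wrong. What is unclear there is the date: with no postbaseline scan, the last valid assessment can only be the screening scan, which precedes Day 1.

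**Size if the Day 1 row were used.** Let k be the number of participants in the first two cases, n the cohort size and s the number still event-free after time t. Assume no other censoring up to t.

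- Deaths as events: S(t) = s/n.
- Deaths censored at Day 1: S(t) = s/(n-k).
- Ratio once all k deaths have occurred: n/(n-k).

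The planned n is 60 in Cohort A and 90 in Cohort B. The share k/n is not in the documents; I assume about 5%, 10% or 15%.

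| Cohort | k | n/(n-k) |
|---|---|---|
| A | 3, 6, 9 | 60/57 = 1.053, 60/54 = 1.111, 60/51 = 1.176 |
| B | 5, 9, 14 | 90/85 = 1.059, 90/81 = 1.111, 90/76 = 1.184 |

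In Cohort A an estimate that should be 0.50 would read 0.53, 0.56 or 0.59. Before the deaths occur the bias can run very slightly the other way. With n = 60, k = 3 and two other events first, it is 58/60 = 0.967 with deaths as events and 55/57 = 0.965 with Day 1 censoring. After the three deaths it is 55/60 = 0.917 against 55/57 = 0.965.

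**The median.** Take the point where the correct curve first reaches 0.50 or below. The reported median moves only if the curve's value there exceeds 0.5(n-k)/n, which for Cohort A is 0.475, 0.450 or 0.425. Two examples with n = 60, three deaths before day 63 and PD found at scans on days 63, 126, 189 and 252:

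- PD counts 18, 10, 8, 6: after day 126, 60 - 3 - 18 - 10 = 29 remain. The estimate is 29/60 = 0.483 with deaths as events and 29/57 = 0.509 with Day 1 censoring. The median moves from 126 to 189 days, and events fall from 45 to 42.
- PD counts 18, 13, 8, 6: 26 remain. The estimate is 26/60 = 0.433 against 26/57 = 0.456, and the median stays at 126 days.

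**The case against.** The best defence is that the surrounding text already supplies the answer. Table 2 works only if a specific row overrides a general one: its no-progression row, read literally, would also take in deaths without PD. A programmer who starts from the PFS definition would use the death row, and there would then be no bias. This shows which reading is right, but the SAP does not state it, and the Day 1 row as worded says the opposite.

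The consequence is also limited. PFS is secondary and descriptive. The planned listings of deaths and of individual PFS (2.6.1 and 2.6.2) would let a reader see how each early death was classified. That makes the point minor; it does not remove it.

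A reader might infer more than the documents support:

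- *That Day 1 censoring is wrong for every death without a scan.* It is not shown to be. Two other rows censor deaths after new anticancer treatment or after two or more missed assessments.
- *That the Day 1 row prevails because it stands earlier in the table.* No order is stated, and strict row order would let the no-progression row absorb deaths before either death row was reached.
- *That "Death between adequate response assessments" leaves the other death row with little use unless it covers the disputed case.* A death after one valid and one missed scan also needs that other row.
- *That the group's size is known.* Protocol Table 16 provides for participants "who discontinued from treatment without post-treatment tumor assessments", so the group need not be empty, but that phrase concerns stopping treatment, not death. The 10.3% of participants with fatal TEAEs on continuous dosing (Protocol section 2.3) counts deaths at any time. The scan due at end of treatment (Protocol Table 3) would make the group smaller.

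**Conclusion.** The point holds in a limited form. The Day 1 row is wrong as worded for participants who die without earlier PD, with no valid postbaseline assessment, fewer than two missed assessments and no new anticancer treatment. For them the SAP's own definition requires an event on the date of death.

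The harm is conditional: it arises only if the Day 1 row is the one applied. The multipliers of about 1.05 to 1.18 rest on the assumed shares and on no other censoring up to that time, and whether the median changes depends on where the curve crosses 0.50. The documents do not show that reported PFS will be biased.

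Nothing else depends on this overlap. ORR already keeps participants without assessments in its denominator, OS has its own rule, a responder must have a valid postbaseline assessment so DOR is untouched, and the sample size rests on ORR. The label is wrong as written, minor.

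**What to change.** Attach one footnote to both Day 1 rows of Table 2, for example: *This row does not cover a participant who dies with no earlier documented PD. That death is an event on its date, with or without a valid postbaseline assessment, unless the row for new anticancer treatment or the row for two or more missed assessments applies. Where one of those two rows applies and there is no valid postbaseline assessment, censor at Day 1.*

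The last sentence fixes the censoring date for deaths that stay censored, which would otherwise point to a scan before first dose. The other rows can stay as they are, and PD without a baseline assessment remains censored as now.

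The cost is one SAP footnote before database lock. No new data are needed, since death dates are already collected for OS. The downside is that PFS may look slightly less favourable than under the Day 1 reading.
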